## **6. Statistical analysis**

The statistical analysis of the data is outlined in each section of the study plan.

## **7. Adverse event reporting**

During the study, the PI will promptly report to the IRB any serious event, defined as a hospitalization, seizure or death. Since this is a minimal risk study, we see no need to establish a DSMB. The PI will not make any changes in the research without IRB approval, except when necessary to eliminate immediate risks to human subjects. The Investigator will also report to the IRB on the progress of the study and adverse events annually.

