there is also a question whether the non- affected hemisphere may interfere with the process of recovery. It is currently not known what factors influence the activity of non- affected hemisphere to either support or interfere with the recovery of stroke. A better understanding of those events is critical to development of optimal therapeutic strategies. For example, non-invasive stimulation of specific areas of the non- affected hemisphere may help to improve functional recovery following stroke. The objectives in this application are to define the factors that influence the activity in the non- affected hemisphere to either support or interfere with the recovery after stroke. We will study the area of the brain that controls movements called motor cortex of the non- affected hemisphere (non- affected motor cortex) as it relates to motor function post-stroke.

In a longitudinal study of stroke patients, non- affected motor cortex reorganization will be assessed in two Specific Aims. In the first Specific Aim, we will determine the extent of functional and structural non- affected motor cortex reorganization using complementary techniques of transcranial magnetic stimulation (TMS), functional and structural MRI of the brain. In the second Specific Aim, the contribution of non- affected motor cortex reorganization to the recovery of motor function will be studied. Repetitive TMS will be used to transiently disrupt non- affected motor cortex function, thereby determine its role for the motor performance of the paretic limb. rTMS related improvement of motor performance would identify a supportive role of contralesional M1 while deterioration of motor performance would indicate its detrimental role. Different rTMS protocols will be applied to non- affected motor cortex to determine

whether non- affected motor cortex can be primed to enhance restorative therapy.

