## **8. Data and safety monitoring plan (DSMP)**

### **8.1. Justification of risk**

According to the recent guidelines about rTMS, the proposed research falls in Class 3 (indirect benefit, low risk): studies in normal subjects and patients that are expected to yield important data on brain physiology or on safety, but have no immediate relevance to clinical problems.

RTMS at 0.1 Hz is below the frequency of most research settings using single TMS and was reported to have no effect on cortical excitability (Chen et al. 1997). TMS applied at a frequency of 0.9 Hz applied over 15 min resulted in decreased cortical excitability of untrained M1 (Chen et al. 1997). Frequencies used in the proposed research (1 Hz and 0.1 Hz) are similar or lower, and are, therefore well below the risk of inducing a seizure (Wassermann 1998b). As the contralesional M1 is targeted, risk should be comparable to normal healthy subjects.

As mentioned above, the proposed TMS protocols are within the recommended safety guidelines. The introduction these safety guidelines (Wassermann, 1998) have proven efficacious in preventing seizures, both in normal subjects and in patients with neurological and psychiatric diseases, despite the fact that such guidelines were based on a relatively restricted sample of normal subjects and considered only conventional rTMS (Rossi et al. 2009; Rossini et al. 1994a; Wassermann 1998a). Furthermore, the use of high frequency/high intensity rTMS was unsuccessful as a non-invasive procedure to activate epileptogenic foci (Tassinari et al. 1990). Subjects are screened (see attached TMS screening form) for, and sign a Consent Form stating that they do not have any metallic (potentially magnetic) material in their body, such as aneurysm clips, pacemakers etc., take drugs that decrease the threshold for a seizure, history of any epileptic seizure. Each subject will be screened with the TMS safety questionnaire used by the PI in previous TMS experiments. Each TMS stimulus produces a loud click and all subjects are issued with ear protectors, so as to avoid potential hearing damage. Since the non- affected hemisphere of patients after stroke is stimulated, the risk should be comparable to the risk of healthy subjects (Hummel et al. 2008). In the event the subject

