has a device implanted that is not described in any of their medical records we may consider to obtain a plain x- ray. The x- ray will be taken of the body part that is affected by the device and will ensure the safety for MRI.

For devices that are safe in the MRI and TMS environment but require preparation prior to TMS or MRI, we will contact treating physician and proceed as recommended by the physician and device manufacturer.

For subjects with loop recorders, we will contact the treating cardiologist to download the data prior to TMS and MRI to prevent the possibility of MRI and TMS related loss of data.

8.2.

Since this is a minimal risk study, we see no need to establish a DSMB. The PI will not make any changes in the research without IRB approval, except when necessary to eliminate immediate risks to human subjects.

8.3. Stopping rules:

If any subject develops a seizure whether related or unrelated to the TMS, these subjects will be excluded from the participation in the experiments. The research projects involving TMS will be stopped if subjects develop a seizure that is related to the TMS until continuation of experiments is approved by the IRB.

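### Prompt IRB reporting is a closed list of three events, so a serious harm outside it has only the annual report as its written route to the IRB

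*Combined protocol and SAP*

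**What the plan says.** Section 7 sets two reporting speeds. For the fast one, the investigator must promptly notify the IRB of "any serious event, defined as a hospitalization, seizure or death". For the slow one, the investigator is to "report to the IRB on the progress of the study and adverse events annually". The same section adds "Since this is a minimal risk study, we see no need to establish a DSMB", and Section 8.2 repeats this. Section 8.3 holds the only stopping rule, and its trigger is a seizure.

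Section 8.1 discusses two kinds of harm that are not on the fast list:

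- **Hearing.** The coil makes a loud click, so "all subjects are issued with ear protectors, so as to avoid potential hearing damage".
- **Implanted devices.** Subjects are screened for metal and implants. An x-ray may be taken for an undocumented device. Devices that need preparation are handled on the advice of the treating physician and the manufacturer. Loop-recorder data are downloaded first "to prevent the possibility of MRI and TMS related loss of data".

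Each has a preventive step. Neither has a reporting step for the case where prevention fails.

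**The concern.** A reporting definition that names three outcomes and stops there sorts events by those outcomes alone. Hearing loss after stimulation, a device that no longer works properly, or a disability that does not resolve can each be serious without an admission, a seizure or a death. Under Section 7 as written, such an event falls into the slow stream together with trivial complaints.

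What is at stake is when the IRB learns of it. With no DSMB, the IRB is the only body outside the study team that the protocol gives a part in safety review. If it hears of an unexpected lasting harm only at the next annual report, other participants may have been stimulated in the meantime without the IRB having had the chance to consider it.

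**Working it through.** No arithmetic underlies the rule, and the protocol states no event rate to reproduce. The check is a reading of the relevant sections together.

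**1. Is the list closed?** Section 7 introduces the three events as a definition. Nothing marks them as examples, and there is no further clause for life-threatening events, disability or unanticipated problems. It is closed.

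**2. Is there a second prompt route in the text?** Section 7's only other reporting provision is the annual one. Section 8.3 requires IRB approval before TMS work resumes, but only after a TMS-related seizure, which is already on the list. Section 7 also bars changes to the research without IRB approval, except to remove immediate risk. A planned change made in response to a harm would therefore reach the IRB early. That depends on the investigator deciding to change something; it is not a duty to report the event.

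**3. Where does each harm go?**

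| Event, with no admission, seizure or death | Treatment in the documents | Written route to the IRB |
|---|---|---|
| Hearing injury | Named as a risk in Section 8.1; ear protection issued | Annual report |
| Implanted-device problem | Preventive steps in Section 8.1; the only consequence named is loss of loop-recorder data | Annual report |
| Unexpected persistent disability | Not addressed | Annual report |
| Any of these leading to admission | On the Section 7 list | Prompt |

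**4. How long is the delay?** Annual reports are 12 months apart. An event just before a report waits almost no time, and one just after it waits close to 12 months. The range is 0 to 12 months, and 12 is the maximum, not the expected value. The documents give no incidence for any of these harms, so the number of reports affected cannot be estimated.

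**The case against.** The case for leaving Section 7 alone has five parts.

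- **The study calls itself minimal risk**, and Section 8.1 places it in a low-risk class with preventive measures for the risks it names. This stands as a reason to expect few such events. It does not say how one should be reported when it happens, and rarity also keeps the cost of a wider definition small.
- **The investigator's team would know at once** and may act on an immediate risk. This stands too: a delay in IRB notice is not a delay in the investigator's awareness. It does not replace independent notice.
- **Other rules may apply.** Institutional reporting policy, the consent form and the eIRB attachments are not available here. This stands in full and limits the conclusion to what the protocol itself writes down.
- **Device malfunction is not a harm the protocol spells out.** Correct. Beyond screening and preparation, the only device consequence named is lost recorder data, so the device example rests on the absence of a reporting step.
- **A broader seriousness definition is a preference.** In part it is: no section contradicts Section 7. But the rule is an explicit one that, followed exactly, delays notice of a serious harm.

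A reader might also infer that the protocol itself expects stimulation to worsen hand function beyond the session, because Section 2 says that "deterioration of motor performance would indicate its detrimental role". The documents do not support that. The sentence tells the analyst how to interpret an outcome. Section 2 puts the duration of the rTMS effect at 10 minutes, and Section 4.4 gives 2-3 hours as the standard visit length (stated for the additional healthy-subject visits). Lasting worsening would be an unexpected event, covered here only under persistent disability.

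**Conclusion.** The point holds as a gap in the written safety plan. A serious harm that involves none of the three listed events has no prompt written route to the IRB and may wait up to 12 months, in a study with no DSMB and a stopping rule confined to seizures. Hearing injury is the clearest example, because the protocol names the risk itself.

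The conclusion assumes that Section 7 is applied as worded and that no outside rule overrides it; the second cannot be checked from the documents.

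Two further inferences should be resisted. One is that all such harms wait for the annual report: any that leads to admission is promptly reportable. The other is that the planned experiments measure how much exposure would accumulate during a delay. Section 4.4 includes sham among the conditions, so a count of experiments is not a count of active sessions.

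No estimate, alpha level, power or sample size is affected. It is a change worth making, and nothing in the documents shows that harm has occurred.

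**What to change.** Extend the definition in Section 7 by one sentence, so that prompt reporting also covers life-threatening events, persistent or significant disability, hearing injury and malfunction of an implanted device. The present three events stay on the list. If institutional rules already require this, Section 7 should say so and refer to them.

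The sentence should govern reporting only. The clinical response, including any effect on a participant's further sessions, stays with the investigator and the IRB. No separate trigger for motor worsening is proposed: it would need a threshold and a comparison time that the documents do not supply, in patients whose motor function is changing after stroke.

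The cost is one sentence in an amendment and a few more prompt reports. The analysis does not change.

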## **8. Data and safety monitoring plan (DSMP)**

### **8.1. Justification of risk**

According to the recent guidelines about rTMS, the proposed research falls in Class 3 (indirect benefit, low risk): studies in normal subjects and patients that are expected to yield important data on brain physiology or on safety, but have no immediate relevance to clinical problems.

RTMS at 0.1 Hz is below the frequency of most research settings using single TMS and was reported to have no effect on cortical excitability (Chen et al. 1997). TMS applied at a frequency of 0.9 Hz applied over 15 min resulted in decreased cortical excitability of untrained M1 (Chen et al. 1997). Frequencies used in the proposed research (1 Hz and 0.1 Hz) are similar or lower, and are, therefore well below the risk of inducing a seizure (Wassermann 1998b). As the contralesional M1 is targeted, risk should be comparable to normal healthy subjects.

As mentioned above, the proposed TMS protocols are within the recommended safety guidelines. The introduction these safety guidelines (Wassermann, 1998) have proven efficacious in preventing seizures, both in normal subjects and in patients with neurological and psychiatric diseases, despite the fact that such guidelines were based on a relatively restricted sample of normal subjects and considered only conventional rTMS (Rossi et al. 2009; Rossini et al. 1994a; Wassermann 1998a). Furthermore, the use of high frequency/high intensity rTMS was unsuccessful as a non-invasive procedure to activate epileptogenic foci (Tassinari et al. 1990). Subjects are screened (see attached TMS screening form) for, and sign a Consent Form stating that they do not have any metallic (potentially magnetic) material in their body, such as aneurysm clips, pacemakers etc., take drugs that decrease the threshold for a seizure, history of any epileptic seizure. Each subject will be screened with the TMS safety questionnaire used by the PI in previous TMS experiments. Each TMS stimulus produces a loud click and all subjects are issued with ear protectors, so as to avoid potential hearing damage. Since the non- affected hemisphere of patients after stroke is stimulated, the risk should be comparable to the risk of healthy subjects (Hummel et al. 2008). In the event the subject

has a device implanted that is not described in any of their medical records we may consider to obtain a plain x- ray. The x- ray will be taken of the body part that is affected by the device and will ensure the safety for MRI.

For devices that are safe in the MRI and TMS environment but require preparation prior to TMS or MRI, we will contact treating physician and proceed as recommended by the physician and device manufacturer.

For subjects with loop recorders, we will contact the treating cardiologist to download the data prior to TMS and MRI to prevent the possibility of MRI and TMS related loss of data.

8.2.

Since this is a minimal risk study, we see no need to establish a DSMB. The PI will not make any changes in the research without IRB approval, except when necessary to eliminate immediate risks to human subjects.

8.3. Stopping rules:

If any subject develops a seizure whether related or unrelated to the TMS, these subjects will be excluded from the participation in the experiments. The research projects involving TMS will be stopped if subjects develop a seizure that is related to the TMS until continuation of experiments is approved by the IRB.

## **9. If applicable: pharmaceutical, biologic, and device information**

For the product manual please refer to the eIRB submission, device information. For

guidelines regarding safety of TMS please refer to the attachments in the eIRB (Rossi et al. 2009; Wassermann 1998b).

